Evaluate the safety and tolerability profile of KRN23 in the treatment of children with XLH (aged 1 to ≤ 12 years), including adverse events (AEs) (eg, nephrocalcinosis), as compared with active control, and immunogenicity profile

Treatment Extension Period Objective:

To evaluate the long-term safety and efficacy of KRN23

STUDY DESIGN AND METHODOLOGY:

UX023-CL301 is a multicenter, randomized, open-label, Phase 3 study comparing the efficacy and safety of KRN23 with active control (oral phosphate/active vitamin D therapy) in children with clinical evidence consistent with XLH (aged 1 to ≤ 12 years), including demonstrated hypophosphatemia, radiographic evidence of rickets (≥ 2.0 points RSS total score), and *PHEX* mutation or variants of uncertain significance. Patients will also be required to have open epiphyses and have received oral phosphate/active vitamin D therapy for ≥ 12 consecutive months (for children ≥ 3 years of age) or ≥ 6 consecutive months (for children < 3 years of age) 7 days prior to the Randomization Visit. Approximately 60 subjects will be randomized 1:1 to receive open-label KRN23 administered by subcutaneous injection or oral phosphate and active vitamin D therapy for a total of 64 weeks in the Treatment Period. Randomization will be stratified by baseline rickets severity (RSS total score ≤ 2.5 vs > 2.5) and age (< 5 vs ≥ 5 years). At least 20 subjects aged 1 to < 5 years will be included (approximately 10 in each treatment arm), and no more than 10 subjects between the ages of 1 to < 3 years will be enrolled. The age range of eligible subjects will be monitored for enrollment for age distribution. No more than 70% female subjects will be enrolled. All subjects will washout of oral phosphate and active vitamin D therapy for 7 days prior to randomization.

Treatment Period (Weeks 0 – 64) – All Subjects

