For subjects in Japan and Korea, the Week 64 visit at the end of the Treatment Period will be the End of Study (EOS) Visit ("Week 64/EOS I"); subjects in these countries will be enrolled into a separate clinical trial of KRN23 or will receive KRN23 through another mechanism. Post-study safety follow-up calls and safety visits will occur only for subjects who are not documented to be continuing on KRN23 at the Week 64/EOS I Visit. A safety follow-up telephone call will occur at 5 weeks (+5 days) after the Week 64/EOS I Visit to determine if KRN23 therapy has been started in another clinical trial or through another mechanism; if KRN23 therapy has not been started, information on any ongoing or new AEs, SAEs, or concomitant medications will be collected. For subjects who do not continue KRN23 therapy, an additional safety visit will occur 12 weeks ±1 week after the last dose of study drug. Every reasonable effort should be made to have required subjects return to the clinic for the final safety visit; however, subjects who are unable to return to the clinic for the final safety visit will be given the option of providing blood and urine samples as part of a Home Health visit.

Treatment Extension Period (Weeks 66 – 140) – Subjects in Europe, the US, Canada, and Australia

After completion of the 64-week Treatment Period, subjects in Europe, the US, Canada, and Australia who were randomized to KRN23 will continue treatment with KRN23 at their previous dose and regimen in the Treatment Extension Period. Subjects in Europe, the US, Canada, and Australia who were randomized to active control will cross over to receive KRN23 at the starting dose and regimen administered to subjects in the KRN23 arm (starting dose of 0.8 mg/kg Q2W; dose may be increased to 1.2 mg/kg Q2W).

Before their first dose of KRN23 at Week 66, subjects who were in the active control arm in the Treatment Period will discontinue treatment the day after the Week 64/EOS I visit to allow washout of oral phosphate and active vitamin D treatments. These subjects must have serum phosphorus < 3.2 mg/dL (< 1.03 mmol/L) (ie, below the lower limit of normal) to continue on study and receive KRN23 in the Treatment Extension Period. If hypophosphatemia is not observed, the subject should be retested for serum phosphorus within a week to ensure that the test result was not due to a technical issue. If hypophosphatemia is still not observed after test and retest, the subject will be discontinued

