9. For the PROMIS Pediatric Pain Interference, Fatigue, and Physical Function Mobility scales, the parent or legal guardian will complete a Parent/Legal Guardian form for subjects ages 5 to < 8 years of age at the Screening Visit. Subjects ≥ 8 years of age at the Screening Visit will complete a pediatric self-report form. Parent/Legal Guardian forms will be used for the duration of the study for subjects < 8 years of age at the Screening Visit who had a baseline assessment, even when a subject turns 8 during the study. If a subject ≥ 8 years of age at screening has difficulty completing the PROMIS self-report, the investigator may allow the PROMIS interview to be administered by trained clinic staff or allow the parent to complete the PROMIS Parent Proxy version. The reason should be carefully documented and consistent practice of administration should be maintained for every visit from Baseline.
10. If a subject is < 5 years of age at the Screening Visit and therefore has no baseline data, SF-10 will not be administered even when the subject turns 5 during the study.
11. Blood and urine to be collected after a minimum overnight fasting time of 4 hours and prior to drug administration (if applicable). Record fasting duration on CRF. Serum phosphorus may be collected as an unscheduled laboratory assessment if necessary. Details for blood and urine collection can be found in the central laboratory manual.
12. Pre- and post-prandial serum phosphorus and calcium concentrations will be assessed at a single clinic visit anytime 10 to 14 days after a KRN23 dose; this clinic visit may take the place of a Home Health visit. Approximately 20 subjects, age ≥ 3 years, will fast overnight for a minimum of 8 hours, and fasting serum will be collected prior to a breakfast containing predefined ranges of phosphate, calories, and carbohydrate representative of a typical Western diet for children. Serum samples will be drawn 1 and 2 hours after the completion of the meal (refer to Table 7.5.4.3.1).

13. Serum KRN23 concentrations and ADA assessment will be performed only for subjects randomized to KRN23 during the Treatment Period and for all subjects during the Treatment Extension Period. If development of anti-KRN23 antibodies is suspected in a given subject, samples may be obtained at additional time points on a case-by-case basis.

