29. For subjects in Europe, the US, Canada, and Australia who complete the ET or EOS II Visit and do not continue on KRN23 on another clinical trial, through commercial use, or through another mechanism, a safety visit will take place 12 weeks \pm 1 week after the last dose of study drug. Every reasonable effort should be made to have required subjects return to the clinic for the final safety visit; however, subjects who are unable to return to the clinic for the final safety visit will be given the option of providing blood and urine samples as part of a Home Health visit. This safety visit will not occur for subjects who are documented to be continuing on KRN23 on a separate clinical trial or another mechanism.
30. Subjects originally randomized to active control will have serum phosphorus assessed at the local laboratory to document hypophosphatemia before administration of the first dose of KRN23. A sample will also be drawn for a serum phosphorus assessment at the central laboratory.

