7.5.3.8.2 Anti-KRN23 Antibody Testing

To determine the immunogenicity profile of KRN23 in children with XLH, blood samples will be obtained for anti-KRN23 antibody (anti-drug antibodies [ADA]) testing at Baseline, and at Weeks 4, 8, 16, 24, 40, 64/EOS I, 88, 112, and 140/EOS II (or Early Termination). The formation of anti-KRN23 antibodies in human serum will be determined using a validated ECLA and a 2-tiered strategy: screening assay and specificity confirmation assay. If the development of anti-KRN23 antibodies is suspected in a given subject, samples may be obtained at additional time points on a case-by-case basis, if warranted. Subjects randomized to active control will not have blood samples drawn for this assessment during the Treatment Period; during the Treatment Extension Period, blood samples for ADA will be drawn on the same schedule as subjects originally randomized to KRN23, ie, Weeks 88, 112, and 140/EOS II.

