8.8.10 Anti-KRN23 Antibody Testing

Anti-KRN23 antibody will be summarized descriptively by treatment group. Shift table from baseline to post-baseline visit will also be provided.

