15. At every Home Health visit for subjects in the KRN23 treatment arm, all subjects randomized to the active control arm will receive a phone call to assess adverse events and concomitant medications. Home Health visits are not applicable to subjects in Japan or Korea.
16. Serum chemistry panels may include PD parameters (i.e. serum phosphorus and ALP), and safety parameters of interest (i.e. calcium) to avoid duplication of testing.
17. Both 2-hr and 24-hr urine will be used for measurements of urinary phosphorus, creatinine, lipase, amylase, and calcium; 2-hr urine will be used for the derivation of TmP/GFR and TRP. For subjects < 5 years of age, spot urine may be collected in place of the 2-hr urine samples for measurements of urinary calcium, phosphorus, and creatine.
18. Separate dental assessments are not required and will be captured under AEs as dental issues arise. At each clinic visit, an oral examination will be conducted and subjects will be proactively asked if they had any dental events from dental caries, delay in eruption of the dentition, enamel hypoplasia, dental abscesses, and gingivitis.
19. HAHA assessment will be performed only for subjects randomized to KRN23. If development of anti-KRN23 antibodies is suspected in a given subject, samples may be obtained at additional timepoints on a case by case basis.
20. Pregnancy testing will be performed on any female subject of childbearing potential who has experienced menarche.
21. An additional safety visit will take place 12 weeks ± 1 week after the date of the last study drug administration for those subjects who discontinue treatment, or 12 weeks ± 1 week after the Week 64 visit for subjects who complete the study and choose not to enroll in an extension study. This visit is not required for subjects who are eligible and choose to take part in an extension study. Every reasonable effort should be made to have required subjects return to the clinic for the final safety visit; however, subjects who are unable to return to the clinic for the final safety visit will be given the option of providing blood and urine samples as part of a Home Health visit.

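### Controls who cross over to KRN23 at Week 66 have no scheduled anti-drug antibody sample before their first dose, so a confirmed positive in the extension could not be classed as pre-existing or treatment-emergent

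*Protocol*

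**What the plan says.** Protocol Section 7.5.3.8.2 lists ADA samples at Baseline, at six visits from Week 4 to Week 64/EOS I, and in the extension. It then sets the control arm apart: "Subjects randomized to active control will not have blood samples drawn for this assessment during the Treatment Period". For the extension it says of these children that "ADA will be drawn on the same schedule as subjects originally randomized to KRN23, ie, Weeks 88, 112, and 140/EOS II". Footnote 13 to the schedule of events says the same: "ADA assessment will be performed only for subjects randomized to KRN23 during the Treatment Period and for all subjects during the Treatment Extension Period". In Table 2.3 the ADA row is marked at Weeks 88, 112, 140/EOS II and the ET visit, and is blank at Weeks 66 and 68.

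The Synopsis gives the timing of the first crossover dose in the sentence that begins "Before their first dose of KRN23 at Week 66, subjects who were in the active control arm". At that visit a local phosphorus test confirms hypophosphatemia before dosing, and the Synopsis adds: "A sample will also be drawn for a serum phosphorus assessment at the central laboratory".

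SAP Section 8.8.10 plans a descriptive ADA summary and says: "Shift table from baseline to post-baseline visit will also be provided". Footnote 19 of SAP Appendix 3 limits the population: "HAHA assessment will be performed only for subjects randomized to KRN23".

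**The concern.** Children randomized to KRN23 have an ADA value from before treatment. Children who start KRN23 by crossing over do not. Without one, a positive result after treatment starts has two explanations that the data cannot separate: reactivity that was already there, or antibodies that developed on KRN23. Counting such a result as treatment-emergent could overstate immunogenicity; leaving it out could understate it.

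The immunogenicity profile is part of the stated safety objective, and the extension has long-term safety as an objective. A pre-dose sample that was never taken cannot be recovered once the first dose has been given.

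**Working it through.** **1. Timeline for a crossed-over control.**
- First KRN23 dose: Week 66 (Synopsis; Protocol Section 7.1).
- First scheduled ADA sample: Week 88 (Section 7.5.3.8.2; Table 2.3).
- Gap: 88 − 66 = 22 weeks.
- Scheduled every-2-week doses before that sample: Weeks 66, 68, …, 86, which is (86 − 66)/2 + 1 = 11 doses.

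The 22 weeks is the scheduled gap, not a universal one. The extension ends on calendar dates, so a late enrollee may reach EOS II before Week 88, and a child who stops early has an ET visit. Both come after dosing has begun.

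**2. Could another planned sample serve as the pre-dose value?**
- Baseline: the Synopsis heads the controlled phase "Treatment Period (Weeks 0 – 64) – All Subjects", so Week 0 falls inside the period from which controls are excluded. Footnote 13 is attached to the ADA row that carries the Baseline mark, and SAP footnote 19 makes no exception for Baseline.
- Extra samples: Section 7.5.3.8.2 allows them case by case, but only when antibodies are already suspected.
- Stored serum: controls give blood for other tests before Week 66, but the documents plan no ADA testing of it.

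**3. The plan's own number.** The documents give no figure for ADA. The only planned number used here is 60 subjects, 30 per arm (Protocol Section 7.6.1), and it reproduces. The standardized difference is (1.80 − 1.40)/0.50 = 0.80. A two-sample t-test at two-sided 0.05 with 80% power needs 25.5, so 26, per arm. Then 26/(1 − 0.10) = 28.9, so 29 per arm or 58 in total, close to 60.

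**4. Share of exposed children without a pre-dose ADA sample.** Let j be the number of controls in Japan and Korea, who leave at Week 64, and d the control drop-out. Then c = (30 − j)(1 − d) controls cross over. All 30 children randomized to KRN23 count as exposed, so the share is c/(30 + c). The documents do not give j, so 2 to 8 is an assumption. The plan's 10% drop-out is used as the upper value of d.

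| j | d | c | share |
|---|---|---|---|
| 0 | 0 | 30 | 30/60 = 50.0% (ceiling) |
| 0 | 10% | 27 | 27/57 = 47.4% |
| 2 | 0 | 28 | 28/58 = 48.3% |
| 8 | 0 | 22 | 22/52 = 42.3% |
| 2 | 10% | 25.2 | 25.2/55.2 = 45.7% |
| 8 | 10% | 19.8 | 19.8/49.8 = 39.8% |

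Controls whose phosphorus is not below 3.2 mg/dL on test and retest are discontinued, which lowers c further by an unknown amount.

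**5. Which results are ambiguous.** The assay has a screening step and a specificity confirmation step, so only a confirmed positive is in question. A negative extension result needs no baseline to be read. No titre step is described, so the plan offers no rise in titre as a substitute for a baseline.

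**The case against.** **The schedule may already cover controls.** Table 2.1 puts Week 0 under a Screening/Baseline heading, separate from the Treatment Period columns, and marks ADA there. A site could read that as a draw for every child. The layout is ambiguous, but the Weeks 0 to 64 heading and both footnotes point the other way. Even on the generous reading, the protocol leaves the point to the site.

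**The omission was deliberate.** The amendment's stated reason is that ADA testing is not needed in controls during the Treatment Period. That is reasonable for the controlled comparison. It does not address the last untreated sample as the reference for later KRN23 exposure, although the protocol does add crossover-specific assessments at Week 68 (KRN23 concentration, weight, physical examination).

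**No stated analysis breaks.** This objection stands. A reader might infer from the SAP's shift table that a planned endpoint cannot be built. The SAP, however, details the original protocol of 04APR2016, plans analyses at Weeks 40 and 64, treats further KRN23 treatment as a separate extension study, and limits ADA to children randomized to KRN23, who have a Baseline sample. For ADA, the amended protocol promises only a descriptive summary by treatment group (Section 7.6.5).

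**The scale is small.** This also stands. A reader might infer that interpretation is lost for half of all exposed children. Half is the ceiling on missing samples, not on ambiguous results. A reader might also expect 1 to 3 misclassified children, by assuming that 3% to 10% have pre-existing reactivity. The documents give no such rate, and at 3% of 22 to 30 crossovers the expected count is only 0.7 to 0.9. Protocol Sections 5.2.3 and 5.3 report no immunogenicity with KRN23 to date.

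**Group-level information exists.** Baseline ADA in the randomized KRN23 arm estimates the frequency of pre-existing reactivity in the same population. That helps to judge the likely error, but it cannot classify an individual crossover.

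**Conclusion.** The gap is real and limits the interpretation of immunogenicity in the extension period. Crossed-over controls have no scheduled pre-dose ADA value, and any confirmed positive among them would stay unclassified. The children without the sample number at most 30 of 60 exposed, or about 40% to 48% of those exposed under the assumed Japan/Korea numbers and drop-out. How many would have an ambiguous result cannot be estimated from the documents. The controlled-period ADA results do not depend on this point, and neither do power or the efficacy analyses. It is an inexpensive improvement, not a defect in a stated analysis.

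**What to change.** - In Table 2.3 and Section 7.5.3.8.2, add a pre-dose ADA sample at Week 66 for crossovers, taken with the central-laboratory draw already planned. If phosphorus has to be retested, the sample from the first test is still pre-dose.
- State in Section 7.5.3.8.2 or footnote 13 whether controls have a Baseline ADA draw.
- When the SAP is extended to the amended protocol, define the Week 66 sample as the ADA baseline for crossovers, and say how a confirmed positive is reported if that sample is missing.

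The cost is one assay and a slightly larger blood volume per crossover, at most 30 samples, plus a minor amendment. If every sample is taken, the share of exposed children with no scheduled pre-dose ADA value falls from at most 50% to zero. The change helps only children who have not yet had their first KRN23 dose.

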7.5.3.9 Pregnancy Testing

Female subjects of childbearing potential will have urine pregnancy tests throughout the study as indicated in [Table 2.1](#), [Table 2.2](#), and [Table 2.3](#). Females not of childbearing potential are not required to undergo pregnancy testing, including those who have not experienced menarche or are permanently sterile.

Female subjects of childbearing potential with a positive pregnancy test at Screening will not be enrolled in the study.

Additional pregnancy tests will be performed at any visit in which pregnancy status is in question. A serum pregnancy test will be performed in the event of a positive or equivocal urine pregnancy test result, or can be performed if pregnancy test by urine is not feasible.

Experience with KRN23 in pregnant women is limited. The study drug may involve risks to a pregnant female or unborn baby which are currently unknown. Female participants of childbearing potential must consent to use a highly effective method of contraception listed below from the period following the signing of the informed consent through 12 weeks after stopping the study drug. Sexually active male subjects with female partners of childbearing potential must consent to use a condom with spermicide or one of the highly effective methods of contraception listed below from the period following the signing of informed consent through 12 weeks after stopping the study drug.

Highly effective methods of contraception ([CTFG 2014](#)) include:

- Combined (estrogen and progestogen containing) hormonal contraception associated with inhibition of ovulation (eg, oral, intravaginal, transdermal)
- Progestogen-only hormonal contraception associated with inhibition of ovulation (eg, oral, injectable, implantable)
- Intrauterine device (IUD) or intrauterine hormone-releasing system (IUS)

- Bilateral tubal occlusion
- Male sterilization, also called vasectomy
- Sexual abstinence (ie, refraining from heterosexual intercourse during the entire period of risk associated with the study treatments, when this is in line with the preferred and usual lifestyle of the subject)

Refer to Section [8.5.4.3](#) for Pregnancy Reporting requirements.

7.5.3.10 Pregnancy of Subject or Partner

Pregnancies in subjects or partners must be reported within 24 hours of knowledge of the event to Ultragenyx or its designee. Female subjects who, at any time during the study, have a positive serum pregnancy test will be discontinued from the study. The investigator must make every effort to follow the pregnancy of either subject or partner through resolution of the pregnancy (delivery or termination) and report the resolution to Ultragenyx or its designee. In the event of a pregnancy in the partner of a subject, the investigator should make every effort to obtain the female partner's consent for release of protected health information. Refer to the Study Reference Manual for details on the reporting procedures to follow in the event of pregnancy.

7.5.3.11 Concomitant Medications/Therapies

Concomitant medications and therapies will be reviewed and recorded in the subject's CRF at each study visit to the investigational site and during Home Health visits (KNR23 treatment arm only during the Treatment Period). Medications (investigational, prescription, over-the-counter, and herbal) and nutritional supplements taken during the 30 days prior to Screening will be reviewed and recorded. Therapies (physical therapy, occupational therapy as well as mobility and walking devices, including ankle-foot orthosis, braces, cane, crutches, walker, wheelchair etc.) utilized during the 30 days prior to Screening will also be reviewed and recorded. At each subsequent visit, change in medications and therapies since the previous visit will be recorded. A discussion of concomitant medications and therapies is provided in Section [7.4.5](#).

7.5.3.12 Dose-limiting Toxicity

A DLT is defined as the occurrence of any of the following:

- Unexpected SAEs occurring during treatment considered to be either definitely, probably, or possibly related to the investigational product or the active control
- A confirmed serum phosphorus level of ≥ 6.5 mg/dL (defined as hyperphosphatemia) at any time after dosing

If a subject experiences a DLT, the planned dosing for that subject will be evaluated by the Investigator and Medical Monitor. The outcome of this investigation will determine the subjects' continuation or withdrawal from the study.

